Illness or clinical adverse event (as defined according to applicable regulations)	No interference with activity	Some interference with activity not requiring medical intervention	Prevents daily activity and requires medical intervention	ER visit or hospitalization

B. Tables for Laboratory Abnormalities

The laboratory values provided in the tables below serve as guidelines and are dependent upon institutional normal parameters. Institutional normal reference ranges should be provided to demonstrate that they are appropriate.

Serum *	Mild (Grade 1)	Moderate (Grade 2)	Severe (Grade 3)	Potentially Life Threatening (Grade 4)**
Sodium – Hyponatremia mEq/L	132 - 134	130 - 131	125 - 129	<125
Sodium – Hypernatremia mEq/L	144 - 145	146 - 147	148-150	>150
Potassium – Hyperkalemia mEq/L	5.1 - 5.2	5.3 - 5.4	5.5 - 5.6	> 5.6
Potassium – Hypokalemia mEq/L	3.5 - 3.6	3.3 - 3.4	3.1 - 3.2	< 3.1
Glucose – Hypoglycemia mg/dL	65 - 69	55-64	45 - 54	< 45
Glucose – Hyperglycemia Fasting – mg/dL Random – mg/dL	100 – 110 110 – 125	111 – 125 126 – 200	>125 >200	Insulin requirements or hyperosmolar coma
Blood Urea Nitrogen BUN mg/dL	23 - 26	27 – 31	> 31	Requires dialysis
Creatinine – mg/dL	1.5 – 1.7	1.8 - 2.0	2.1 – 2.5	> 2.5 or requires dialysis
Calcium – hypocalcemia mg/dL	8.0 - 8.4	7.5 – 7.9	7.0 - 7.4	< 7.0
Calcium – hypercalcemia mg/dL	10.5 - 11.0	11.1 - 11.5	11.6 - 12.0	> 12.0
Magnesium – hypomagnesemia mg/dL	1.3 – 1.5	1.1 – 1.2	0.9 – 1.0	< 0.9
Phosphorous – hypophosphatemia mg/dL	2.3 – 2.5	2.0-2.2	1.6 – 1.9	< 1.6
CPK – mg/dL	1.25 – 1.5 x ULN***	1.6 – 3.0 x ULN	3.1 –10 x ULN	> 10 x ULN
Albumin – Hypoalbuminemia g/dL	2.8 - 3.1	2.5 – 2.7	< 2.5	
Total Protein – Hypoproteinemia g/dL	5.5-6.0	5.0 - 5.4	< 5.0	
Alkaline phosphate – increase by factor	1.1 – 2.0 x ULN	2.1 – 3.0 x ULN	. 3.1 – 10 x ULN	$> 10 \mathrm{x} \mathrm{ULN}$
Liver Function Tests –ALT, AST increase by factor	1.1 – 2.5 x ULN	2.6 – 5.0 x ULN	5.1 – 10 x ULN	> 10 x ULN
Bilirubin – when accompanied by any increase in Liver Function Test increase by factor	1.1 – 1.25 x ULN	1.26 – 1.5 x ULN	1.51 – 1.75 x ULN	> 1.75 x ULN
Bilirubin – when Liver Function Test is normal; increase by factor	1.1 – 1.5 x ULN	1.6 – 2.0 x ULN	2.0 – 3.0 x ULN	> 3.0 x ULN
Cholesterol	201 - 210	211 - 225	> 226	
Pancreatic enzymes _ amylase linase	$11 - 15 \times 11$ N	$16 - 20 \times III N$	$21 - 50 \times III N$	$> 5.0 \times III N$

Pancreatic enzymes – amylase, lipase $1.1 - 1.5 \times \text{ULN}$ $1.6 - 2.0 \times \text{ULN}$ $2.1 - 5.0 \times \text{ULN}$ $> 5.0 \times \text{The laboratory values provided in the tables serve as guidelines and are dependent upon institutional normal$

parameters. Institutional normal reference ranges should be provided to demonstrate that they are appropriate. ** The clinical signs or symptoms associated with laboratory abnormalities might result in characterization of the laboratory abnormalities as Potentially Life Threatening (Grade 4). For example, a low sodium value that falls within a grade 3 parameter (125-129 mE/L) should be recorded as a grade 4 hyponatremia event if the subject had a new seizure associated with the low sodium value.

***ULN" is the upper limit of the normal range.

**

Hematology *	Mild (Grade 1)	Moderate (Grade 2)	Severe (Grade 3)	Potentially Life Threatening (Grade 4)
Hemoglobin (Female) - gm/dL	11.0 - 12.0	9.5 - 10.9	8.0-9.4	< 8.0
Hemoglobin (Female)	Any decrease – 1.5	1.6 - 2.0	2.1 - 5.0	> 5.0
change from baseline value - gm/dL	32			
Hemoglobin (Male) - gm/dL	12.5 - 13.5	10.5 - 12.4	8.5 – 10.4	< 8.5
Hemoglobin (Male)	Any decrease – 1.5	1.6 - 2.0	2.1 - 5.0	> 5.0
change from baseline value – gm/dL				
WBC Increase - cell/mm ³	10,800 - 15,000	15,001 - 20,000	20,001 – 25, 000	> 25,000
WBC Decrease - cell/mm ³	2,500 - 3,500	1,500 – 2,499	1,000 – 1,499	< 1,000
Lymphocytes Decrease - cell/mm ³	750 - 1,000	500 - 749	250 - 499	< 250
Neutrophils Decrease - cell/mm ³	1,500 - 2,000	1,000 – 1,499	500 - 999	< 500
Eosinophils - cell/mm ³	650 - 1500	1501 - 5000	> 5000	Hypereosinophilic
Platelets Decreased - cell/mm ³	125,000 - 140,000	100,000 - 124,000	25,000 - 99,000	< 25,000
PT – increase by factor	1.0 - 1.10 x	. 1.11 – 1.20 x ULN	1.21 – 1.25 x ULN	>1.25 ULN
(prothrombin time)	ULN**			
PTT – increase by factor	1.0 – 1.2 x ULN	1.21 – 1.4 x ULN	1.41 – 1.5 x ULN	$> 1.5 \mathrm{x} \mathrm{ULN}$
(partial thromboplastin time)				
Fibrinogen increase - mg/dL	400 - 500	501 - 600	> 600	
Fibrinogen decrease - mg/dL	150 - 200	125 – 149	100 - 124	< 100 or associated
				with gross bleeding
				or disseminated
				intravascular
				coagulation (DIC)

ж

The laboratory values provided in the tables serve as guidelines and are dependent upon institutional normal parameters. Institutional normal reference ranges should be provided to demonstrate that they are appropriate. "ULN" is the upper limit of the normal range.

Urine *	Mild (Grade 1)	Moderate (Grade 2)	Severe (Grade 3)	Potentially Life Threatening (Grade 4)
Protein	Trace	1+	2+	Hospitalization or dialysis
Glucose	Trace	1+	2+	Hospitalization for hyperglycemia
Blood (microscopic) – red blood cells per high power field (rbc/hpf)	1 - 10	11 – 50	> 50 and/or gross blood	Hospitalization or packed red blood cells (PRBC) transfusion

The laboratory values provided in the tables serve as guidelines and are dependent upon institutional normal ж parameters. Institutional normal reference ranges should be provided to demonstrate that they are appropriate.

Document: K:\AAA\Ga-PSMA-R2\VYA27826\ Biostatistics\Documentation\SAP\v2.0\Ga-PSMA-R2-SAP_v2.0
Author: [REDACTED] Version Number: 2.0

Version Date: 29JUN2020

Template No.: CS_TP_BS016 Revision 5
Effective Date: 01Apr2018

Reference: CS_WI_BS005

[REDACTED]
Statistical Analysis Plan

Advanced Accelerator Applications
PROTOCOL A206D-A01-001
Page 5 of 48

MODIFICATION HISTORY

Unique Identifier for this Version	Date of the Document Version	Author	Significant Changes from Previous Authorized Version
1.0	23NOV2018	[REDACTED]	Not Applicable – First Version
2.0	29JUN2020	[REDACTED]	
 Section 6.1 - The PCa-BR population group will be presented separately for Phase I and Phase II patients. Section 15.2 – details of data presentations updated.

Document: K:\AAA\Ga-PSMA-R2\VYA27826\ Biostatistics\Documentation\SAP\v2.0\Ga-PSMA-R2-SAP_v2.0
Author: [REDACTED] Version Number: 2.0

Version Date: 29JUN2020

Template No.: CS_TP_BS016 Revision 5
Effective Date: 01Apr2018

Reference: CS_WI_BS005

Statistical Analysis Plan

APPENDIX 4. Vital Signs measurements45

APPENDIX 5. Dosimetry measurements47

Document: K:\AAA\Ga-PSMA-R2\VYA27826\ Biostatistics\Documentation\SAP\v2.0\Ga-PSMA-R2-SAP_v2.0
Author: [Redacted] Version Number: 2.0

Version Date: 29JUN2020
Template No.: CS_TP_BS016 Revision 5 Reference: CS_WI_BS005
Effective Date: 01Apr2018

LIST OF ABBREVIATIONS

AE	Adverse Event
ALT	Alanine aminotransferase
ALP	Alkaline Phosphatase
AST	Aspartate aminotransferase
BLQ	Below the Lower Limit of Quantification
BUN	Blood Urea Nitrogen
CS	Clinically Significant
CT	Computed Tomography
DBP	Diastolic Blood Pressure
ECG	Electrocardiogram
ECOG	Eastern Cooperative Oncology Group
eCRF	Electronic Case Report Form
EG	Enterprise Guide
eGFR	Estimated Glomerular Filtration Rate
ENR	All Patients Enrolled
FAS	Full Analysis Set
⁶⁸ Ga	Gallium radioisotope 68
⁶⁸ Ga-PSMA-R2	⁶⁸ Ga-PSMA ligand
g-GT	Gamma-glutamyl transpeptidase
Hb	Hemoglobin
LDH	Lactic acid dehydrogenase
MBq	Megabecquerel
MCV	Mean corpuscular volume
MedDRA	Medical Dictionary for Regulatory Activities
mPca	Metastatic Stage Prostate Cancer
MRI	Magnetic Resonance Imaging
NCS	Not Clinically Significant
ODS	Output Delivery System
Pca	Prostate Cancer
Pca-BR	Biochemical Recurrence Prostate Cancer
PET	Positron Emission Tomography
PK	Pharmacokinetic(s)
PPS	Per Protocol Set
PR	PR interval of the electrocardiogram; time duration between the P and R waves
PSA	Prostate specific antigen

Document: K:\AAA\Ga-PSMA-R2\VYA27826\ Biostatistics\Documentation\SAP\v2.0\Ga-PSMA-R2-SAP_v2.0
 Author:  Version Number: 2.0

Version Date: 29JUN2020

Template No.: CS_TP_BS016 Revision 5
 Effective Date: 01Apr2018

Reference: CS_WI_BS005

PSMA	Prostate Specific Membrane Antigen
PT	Preferred Term
QRS	QRS interval of the electrocardiogram; duration of the QRS complex
QT	QT interval of ECG, duration between the Q and T waves
QTcB	QT interval of ECG corrected for heart rate using Bazett's formula
QTcF	QT interval of ECG corrected for heart rate using Fridericia's formula
Q1	First Quartile
Q3	Third Quartile
RBC	Red blood cell
RR	Time duration between two consecutive R waves of the electrocardiogram
RTF	Rich Text Format
SAE	Serious Adverse Event
SAP	Statistical Analysis Plan
SAS	Statistical Analysis Software
SBP	Systolic Blood Pressure
SD	Standard Deviation
SOC	System Organ Class
TEAE	Treatment Emergent Adverse Event
ULQ	Upper Limit of Quantification
WBC	White blood cell
WHO-DD	Who Drug Dictionary

Document: K:\AAA\Ga-PSMA-R2\VYA27826\ Biostatistics\Documentation\SAP\v2.0\Ga-PSMA-R2-SAP_v2.0
 Author:  Version Number: 2.0

Version Date: 29JUN2020

Template No.: CS_TP_BS016 Revision 5
 Effective Date: 01Apr2018

Reference: CS_WI_BS005

1. INTRODUCTION

This document describes the rules and conventions to be used in the presentation and analysis of safety data, for Protocol A206D-A01-001. It describes the data to be summarized and analyzed, including specifics of the statistical analyses to be performed.

This statistical analysis plan (SAP) is based on protocol version 2.2, dated 22 February 2018.

2. STUDY OBJECTIVES

2.1. PRIMARY OBJECTIVE

The primary objective is to assess safety and tolerability of a single administration of 3 mega Becquerel (MBq)/kg, but not less than 150 MBq and not more than 250 MBq, of ⁶⁸Ga-PSMA-R2.

2.2. SECONDARY OBJECTIVES

The secondary objectives are:

- To assess the pharmacokinetics (PK) of ⁶⁸Ga-PSMA-R2.
- To assess biodistribution and dosimetry of ⁶⁸Ga-PSMA-R2.
- To establish the optimal imaging method for determining location and burden of positive lesions on ⁶⁸Ga-PSMA-R2 positron emission tomography (PET) imaging in patients in comparison with lesions identified with conventional imaging scans (computed tomography (CT)/magnetic resonance imaging (MRI) and bone scan), and to calculate the agreement of ⁶⁸Ga-PSMA-R2 PET with conventional anatomical/functional imaging on a per patient basis.

3. STUDY DESIGN

3.1. GENERAL DESCRIPTION

This is an open label, multi-center, single dose, Phase I/II study to evaluate the safety and tolerability of 3 MBq/Kg, but not less than 150 and no more than 250 MBq, of ⁶⁸Ga-PSMA-R2 in adult patients with PCa expressing PSMA receptors.

This study will consist of 2 parts.

- During the first part (Phase I), approximately 6 patients with biochemically recurrent PCa will receive the investigational product (IP) and will remain at the site for approximately 6 hours post-administration in order to assess the PK, biodistribution vs. time, and dosimetry for critical organs. Patients will receive a single dose of 3 MBq kg. (≥ 150 and ≤ 250 MBq), of ⁶⁸Ga-PSMA-R2 intravenously. Serial blood and

Document:	K:\AAA\Ga-PSMA-R2\VYA27826\ Biostatistics\Documentation\SAP\v2.0\Ga-PSMA-R2-SAP_v2.0	Version Number:	2.0
Author:	[Redacted]		

Template No.: CS_TP_BS016 Revision 5
Effective Date: 01Apr2018

Version Date: 29JUN2020
Reference: CS_WI_BS005

Statistical Analysis Plan

urine samples will be collected for PK characterization and dosimetry and whole body PET/CT will be acquired at selected time points (0-4 hours) to determine organ and tumor absorbed doses. Safety assessments will be conducted after IP administration on Day 1, and during follow-up on Days 7 and 28.

- In the second part of the study (Phase II), two groups of approximately 12 patients will be enrolled (patients with PCa in biochemical recurrence (PCa-BR), and patients with prostate cancer in the metastatic stage (mPCa)). Enrollment will be capped at 12 patients in each group to ensure an even distribution of patient conditions. If preliminary data analysis from the Phase I part of the study provides sufficient dosimetry data, all patients will undergo whole body PET/CT imaging optimized for time (up to 2 timepoints) according to the data analysis from the Phase I component of the study.

This study is comprised of 4 clinical visits and will be conducted in 3 study periods including: Screening, administration/ imaging, and safety follow-up period (final/early termination).

3.2. SCHEDULE OF EVENTS

Schedule of events can be found in Section "STUDY PROCEDURES AND ASSESSMENTS" of the protocol.

4. PLANNED ANALYSES

The following analysis will be performed for this study:

- Phase I Analysis assessing PK, Biodistribution, Dosimetry and Imaging
- Final Analysis (combining Phase I and Phase II data)

This document will provide details for Phase I Biodistribution, Dosimetry and Imaging Analysis and Final Analysis. All planned analyses identified in this SAP will be performed by [REDACTED] Biostatistics following Database Lock.

4.1. PK ANALYSIS

Phase I PK Analysis will be described in a separate SAP written by the PK specialist from a third-party clinical pharmacokinetics vendor.

Derivation of the PK parameters and the PK summary tables, listings and figures, will be the responsibility of third-party clinical pharmacokinetics vendor.

4.2. BIODISTRIBUTION, DOSIMETRY AND IMAGING ANALYSIS

The biodistribution, dosimetry and imaging analysis will be split in two:

- The analysis using data from the principal scientist from a third-party radiation dosimetry vendor will be performed only for Phase I.
- The analysis using data from a third-party medical imaging vendor will be performed for both Phase I and

Document:	K:\AAA\Ga-PSMA-R2\VYA27826\ Biostatistics\Documentation\SAP\2.0\Ga-PSMA-R2-SAP_v2.0
Author:	[REDACTED] Version Number: 2.0

Version Date: 29JUN2020

Template No.: CS_TP_BS016 Revision 5
Effective Date: 01Apr2018

Reference: CS_WI_BS005

Phase II.

Summary tables, listings and figures needed for the biodistribution, dosimetry and imaging are described in section 15.

4.3. FINAL ANALYSIS

The final analysis will be conducted at the end of the study and will include the analyses of safety endpoints. This analysis will be based on the full analysis set (FAS) and may be repeated on the per protocol set (PPS).

5. ANALYSIS SETS

Agreement and authorization of patients included/ excluded from each analysis set will be conducted prior to the final database lock. PK analysis set will be described in the SAP written by a third party clinical pharmacokinetics vendor.

5.1. ALL PATIENTS ENROLLED SET [ENR]

The all patients enrolled (ENR) set will contain all patients who provide informed consent for this study.

5.2. FULL ANALYSIS SET [FAS]

The full analysis set (FAS) will contain all patients who receive at least one dose of study medication. The safety set in this case is identical to the full analysis set and so will not be defined as a separate set.

5.3. PER PROTOCOL SET [PPS]

The per-protocol set (PPS) will contain all patients in the FAS who complete the study according to the protocol with no critical or major protocol deviations. The decisions regarding critical and major protocol deviations, and the definition of the analysis population, will be finalized prior to database lock.

6. GENERAL CONSIDERATIONS

6.1. POPULATION SUMMARIZATION

In general, data will be presented by population.

- The following populations will be used in the analyses:

Document:	K:\AAA\Ga-PSMA-R2\VYA27826\ Biostatistics\Documentation\SAP\v2.0\Ga-PSMA-R2-SAP_v2.0
Author:	[Redacted] Version Number: 2.0
Template No.:	CS_TP_BS016 Revision 5
Effective Date:	01Apr2018
Version Date:	29JUN2020
Reference:	CS_WI_BS005

- PCa-BR
- mPCa
- The PCa-BR population group will also be presented separately for Phase I and Phase II patients.

6.2. REFERENCE START DATE AND STUDY DAY

Study Day will be calculated from the reference start date and will be used to show start/ stop day of assessments and events.

Reference start date is defined as the day of the first and single administration of study medication, (Day 1 is the day of the first and single dose of study medication).

If the date of the event is on or after the reference date, then:

- Study Day = (date of event – reference date) + 1.

If the date of the event is prior to the reference date, then:

- Study Day = (date of event – reference date).

In the situation where the event date is partial or missing, Study Day, and any corresponding durations will appear missing in the listings.

6.3. BASELINE

Unless otherwise specified, baseline is defined as the last non-missing measurement taken prior to reference start date (including unscheduled assessments). In the case where the last non-missing measurement and the reference start date and time coincide, that measurement will be considered pre-baseline, but Adverse Events (AEs) and medications commencing on the reference start date will be considered post-baseline.

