techniques. Tumor uptake will be evaluated by SUV. SUV _{mean} and SUV _{max} will be
determined along with tumor to background ratio and these will be summarized
descriptively. Positive and negative lesions by the two imaging techniques will be
cross tabulated overall and by localization area on a lesion level and a patient level.
Agreement calculations will be performed on a patient level and tests of association
may be performed where appropriate.
Preliminary explorations of ⁶⁸ Ga-PSMA-R2 imaging performance relative to
cytology and/or historiathology findings from archival and/or recent bionsy
specimens will be performed for patients with bionsy data available
speemens will be performed for putents will blopsy dua dvalable.

STUDY PROCEDURES AND ASSESSMENTS

	Screening (Day -14 to Day -1 (+1 day)	Imaging Day 1 (+1 day)	Safety Follow-up Day 7 (+1 day)	Safety Follow-up Day 28 (+1 day)
Informed consent	X			
Inclusion/Exclusion Criteria Assessment	X			
Medical History & Demographics	Х			
ECOG Performance Status	X	Х	X	Х
Standard 12-lead ECG	X	Xª		
Disease Assessment: Imaging (CT/MRI or Bone Scan)	X ^b			
Vital Signs: Temperature (Temp), Blood Pressure (BP), Heart Rate (HR), and Respiratory Rate (RR) ^c	Х	Х	Х	Х
PSA	X			
Lab Analysis: Hematology, Blood Chemistry ^d	X	Х	Х	Х
Urine Analysis (Dipstick) ^e	X	Х	X	Х
⁶⁸ Ga-PSMA-R2 Administration		Х		
⁶⁸ Ga-PSMA-R2 PET/CT (Dosimetry) ^f		Х		
PK and Dosimetry Sample Collection (Blood) ^g		Х		
PK and Dosimetry Sample Collection (Urine) ^h		Х		
Adverse Event Collection	X	Х	X	Х
Concomitant Medications	X	X	X	Х

Table 1 Schedule of Procedures and Assessments

^a On Day 1, 12-Lead ECG will be collected after dosage administration.

^bAll patients are required to undergo a CT/MRI and bone scan if indicated (can be performed ≤ 2 months prior to study entry).

^c On Day 1 vital signs (temp, BP, HR, and RR) will be performed before and after to ⁶⁸Ga-PSMA-R2 injection and also at the end of ⁶⁸Ga-PSMA-R2 PET/CT scan.

^d Peripheral venous blood samples will be collected at each visit. On Day 1, blood samples will be collected after administration of ⁶⁸Ga-PSMA-R2.

^e A urine sample will be collected at each visit and analyzed at the clinical site if dipstick results are abnormal. Sample collection on Day 1 will be performed after the administration of IP

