8.2. Analysis Methods

Statistical analysis will be described in detail in the statistical analysis plan prior to database lock.

Due to the single arm design of the study, the primary focus of the statistical analysis will be on descriptive statistics and graphical presentations of data. Continuous variables will be presented as number of non-missing values, mean, standard deviation, median, minimum, maximum and quartiles. For categorical variables, descriptive statistics will include counts and percentages per category. Confidence intervals will be computed when appropriate, usually as 95% intervals, but 80% intervals may also be produced in some instances due to the early phase nature of this trial. Continuous variables will be compared where relevant using the most appropriate test such as paired analysis Mann-Whitney-Wilcoxon U test. Proportions will be compared using the appropriate test among Fisher's exact test or McNemar test. Pearson's or Spearman linear regression analysis will be used to explore potential relationships between two continuous variables as appropriate. Any hypothesis testing that is performed will be interpreted as exploratory and no emphasis will be placed on nominal significance levels. No adjustment for multiplicity will be applied and missing data will not be replaced.

Data presentations will group the PCa-BC and mPCa populations and also include an overall total column.

For analysis purposes, baseline for a given assessment will be defined as the last non-missing value prior to the administration of ⁶⁸Ga-PSMA-R2.

The Full Analysis Set will consist of all patients who enter the study and receive at least one dose of ⁶⁸Ga-PSMA-R2. The safety set in this case is identical to the full analysis set and so will not be de-fined as a separate set. The Per Protocol set consists of all patients in the full analysis set who complete the study according to the protocol with no major protocol violations. All analyses will primarily be performed on the full analysis set, select analyses may be repeated on the per protocol set if there are sufficient violations to warrant it and deviation of results by using the per protocol set will be discussed.

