- The program path and name and version number (if applicable) should appear as footnote 1 at the bottom of the page
- The date/time stamp should appear as footnote 2 at the bottom of the page
- Footnotes should be left-aligned.
- Footnotes should be in sentence case.
- Only "typewriter" symbols are permitted – e.g. "*" , "\$" , "#" , "@" , "&" and "–".

Document: K:\AAA\Ga-PSMA-R2\VYA27826\ Biostatistics\Documentation\SAP\v2.0\Ga-PSMA-R2-SAP_v2.0
 Author: [Redacted] Version Number: 2.0
 Version Date: 29JUN2020
 Template No.: CS_TP_BS016 Revision 5 Reference: CS_WI_BS005
 Effective Date: 01Apr2018

Statistical Analysis Plan

- The choice of footnote symbols should be consistent. E.g. if you have the footnote “# indicates last observation carried forward” for one table, the same symbol and footnote should indicate LOCF for all tables.
- If text wraps across more than one line (for a note), the first letter for all lines of text after the first one will be indented to align beneath the first letter of the text in the first line.
- The page identification in the format Page X of Y (where Y is the total number of pages for the output) should appear in the footer, right aligned.

Ordering of footnotes should be as follows:

- 1.) Source data listing reference, if necessary
 - 2.) Abbreviations and definitions
 - 3.) Formulae
 - 4.) P-value significance footnote
 - 5.) Symbols
 - 6.) Specific notes
- Common notes from table to table should appear in the same order.

The symbols should appear in the same order as what they are defined in the table or listing, from left to right.

DATES & TIMES

Depending on data available, dates and times will take the form yyyy-mm-ddThh:mm:ss.

SPELLING FORMAT

English US.

PRESENTATION OF POPULATION GROUPS

For outputs, population groups will be represented as follows and in that order:

Population Group	For Tables, Listings and Graphs
PCa-BR	PCa-BR
mPCa	mPCa
PCa-BR + mPCa	Overall

PRESENTATION OF VISITS

For outputs, visits will be represented as follows and in that order:

Document: K:\AAA\Ga-PSMA-R2\VYA27826\ Biostatistics\Documentation\SAP\v2.0\Ga-PSMA-R2-SAP_v2.0
 Author: [Redacted] Version Number: 2.0
 Version Date: 29JUN2020
 Template No.: CS_TP_BS016 Revision 5 Reference: CS_WI_BS005
 Effective Date: 01Apr2018

Statistical Analysis Plan

Long Name (default)	Short Name
Screening	Screening
Baseline (Day 1)	D1
Day 7	D7
Day 28	D28

LISTINGS

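### SAP 6.3 does not settle whether the Day 1 pre-injection vital signs or the Screening values are baseline, and so does not clearly match protocol 8.2

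*SAP*

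**What the plan says.** - **Protocol 8.2 (Analysis Methods):** "baseline for a given assessment will be defined as the last non-missing value prior to the administration of" the study drug. The anchor is the administration.
- **SAP 6.3, first sentence:** unless otherwise specified, "baseline is defined as the last non-missing measurement taken prior to reference start date (including unscheduled assessments". The anchor is the reference start date.
- **SAP 6.2:** "Reference start date is defined as the day of the first and single administration of study medication". The Study Day rule then uses it as a calendar date: "If the date of the event is on or after the reference date, then" one is added to the difference in days, so everything on the day of dosing is Day 1.
- **SAP 6.3, second sentence:** "In the case where the last non-missing measurement and the reference start date and time coincide, that measurement will be considered pre-baseline". The rest of that sentence places adverse events and medications that start on the reference date after baseline. It says nothing of the kind about measurements.
- **SAP Appendix 1, Presentation of Visits:** the dosing visit carries the label "Baseline (Day 1" (closing bracket omitted here).
- **SAP 14.4 (Vital Signs):** gives no baseline rule of its own, so 6.3 governs. It calls for change from baseline by visit and for the incidence of markedly abnormal values at any post-baseline time.
- **Protocol Table 1 (footnote c) and protocol 6.3:** Day 1 vital signs are taken before injection, after injection and at the end of the PET/CT scan.
- **Protocol Table 1 footnotes, 6.5.3 and 6.5.5.1:** Day 1 laboratory samples and ECG are taken after administration.

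**The concern.** The two documents anchor baseline to different things: a moment in the protocol, a calendar day in the first sentence of the SAP rule. The difference has no effect unless something is measured on the dosing day before the injection. One scheduled assessment is: the pre-injection vital signs.

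Change from baseline in vital signs is among the primary endpoints in protocol 2.2.1 and SAP 14. If one programmer follows the first sentence of SAP 6.3 and another follows protocol 8.2, they will derive different baselines from the same data. In the first case, changes after the injection are measured from a reading that may be up to 14 days old (protocol 6.2: Day -14 to Day -1), although a same-day pre-drug reading is available. An abnormality already present before the injection might also be tabulated as if it had arisen afterwards.

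**Working it through.** The plan gives no figure to reproduce. The check classifies each scheduled assessment under each reading of the rules.

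**Step 1. The Day 1 pre-injection reading.**

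| Reading | Is the pre-injection value baseline? | Why |
|---|---|---|
| Protocol 8.2 | Yes | It is the last value before administration. |
| SAP 6.3 first sentence with SAP 6.2 (day level) | No; Screening is used, or a later unscheduled value from before Day 1 | Study Day = 0 + 1 = 1, so the reading falls on the reference date and not before it. |
| SAP 6.3 with its second sentence taken as a date-and-time rule | Yes | If a value at the moment of dosing is on the pre-drug side, an earlier one must be too. |

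The second sentence does not by itself rescue the day-level reading. It covers only a measurement that coincides with dosing, and a reading taken minutes earlier does not coincide. It also uses the term *pre-baseline*, which the SAP does not define and which is not the same as calling the value baseline.

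**Step 2. Laboratory tests and ECG.** The scheduled Day 1 samples and ECG follow the injection. The last scheduled value before dosing is Screening under all three readings, so nothing changes.

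**Step 3. Effect on change from baseline.** For any later value X:

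(X − Screening) − (X − pre-injection) = pre-injection − Screening

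Every later change for a patient moves by that one difference. The documents do not say how large it is. If it were assumed to be 5, 10 or 20 mmHg for systolic pressure, every later systolic change for that patient would move by 5, 10 or 20 mmHg.

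**Step 4. Number of post-baseline sets.** Scheduled sets per patient: Screening 1 + Day 1 3 + Day 7 1 + Day 28 1 = 6.

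- Protocol 8.2, baseline = pre-injection: 2 + 1 + 1 = 4 sets after baseline.
- Day-level reading, baseline = Screening: 3 + 1 + 1 = 5 sets after baseline, of which 1 precedes the drug.
- For the planned maximum of 30 patients: 30 × 4 = 120 against 30 × 5 = 150, and 30/150 = 20% of the latter are pre-drug.

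These counts show how many readings would be classified differently. They are not error rates. The step from a Screening baseline to counting the pre-injection set as post-baseline is an inference, because the SAP does not say so.

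**The case against.** The strongest reply is that SAP 6.3, read as a whole, already agrees with the protocol. Its second sentence refers to a time as well as a date, which would have no function under a day-only rule. A day-only rule also gives an incoherent result: a value at the instant of injection would be on the pre-drug side, while one taken minutes before would not. The Appendix 1 label ties baseline to Day 1, and the SAP declares its source: "This statistical analysis plan (SAP) is based on protocol version 2.2, dated 22 February 2018". This reply largely stands as evidence of intent; a date-and-time rule is probably what was meant. It does not supply the rule. The second sentence covers only exact ties, and the label conflicts with the first sentence of 6.3 and names a visit that also holds post-dose vital signs, laboratory tests and ECG.

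A second reply is that the harm is limited. SAP 14.4 also provides by-visit shift tables and a listing of patients with markedly abnormal values, so a reader would not depend on the incidence table alone. That stands too.

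Three stronger readings are tempting, and the documents do not support them:

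- **That the SAP classes the pre-injection reading as post-baseline.** No sentence says this. On the dosing day, 6.3 puts only adverse events and medications after baseline.
- **That laboratory and ECG baselines are also at risk,** because Table 1 adds a one-day allowance to the Screening window. The heading of protocol 6.2 ends Screening at Day -1, and the same allowance stands in all four column heads of Table 1. Nothing states that screening tests may be done on the dosing day.
- **That SAP 14.4 fails to separate the three Day 1 readings.** SAP 8 leaves table content to templates that were not available for this review, so this cannot be judged.

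**Conclusion.** The point holds as an inconsistency within SAP 6.3 that leaves the SAP not clearly in line with protocol 8.2. Applied as written, the first sentence of 6.3 replaces the Day 1 pre-injection vital signs with Screening as baseline. The surrounding text suggests that this was not intended, but does not correct it.

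The scope is temperature, blood pressure, heart rate and respiratory rate, in patients who have a recorded pre-injection value. The effect on each later change is exactly the pre-injection value minus the Screening value, of unknown size. By inference, one extra pre-drug set per patient (5 instead of 4) could enter the post-baseline incidence. This assumes the scheduled visits only, no unscheduled pre-dose values, and no overriding rule in the output templates.

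It is worth correcting because it touches a primary safety endpoint and the correction is nearly free. All analyses are descriptive, so no test, threshold or decision depends on it.

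**What to change.** In SAP 6.3:

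1. Define baseline as the last non-missing value before the date and time of administration, in line with protocol 8.2.
2. State that values taken on the dosing day before the injection qualify.
3. Replace the *pre-baseline* wording with a plain statement of whether a value timed exactly at the injection may serve as baseline.

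Optionally, rename the Appendix 1 visit to Day 1, since that visit also contains post-dose vital signs, laboratory tests and ECG.

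The cost is one or two sentences and, if adopted, one label. No new assessment is needed, because the pre-injection reading is already scheduled. The edit should be made before the baseline derivation is programmed; if it is already programmed, the code should be checked against protocol 8.2.
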